### *3.5 Anesthesia*

Patients will receive general anesthesia.

### *3.7 Primary endpoint*

Mesocolic Resection Plane. Occurrence of Mesocolic Resection Plane. If such an episode occurs, then it will be defined as=1 'YES' If such an episode does not occur, then it will be defined as=0 'NO'. [Time Frame: 1 month postoperatively]

### *3.8 Secondary endpoints*

Secondary endpoints of the present study are:

Open Conversion. Occurrence of Open Conversion. If such an episode occurs, then it will be defined as=1 'YES' If such an episode does not occur, then it will be defined as=0 'NO'. [Time Frame: Intraoperative period]

Operative Time. The total operative time will be recorded. Measurement unit: minutes [Time Frame: Intraoperative period]

Type of Anastomosis. Occurrence of Stapled or Handsewn Anastomosis. If such an episode occurs, then it will be defined as=1 'YES' If such an episode does not occur, then it will be defined as=0 'NO' [Time Frame: Intraoperative period]

Intraoperative Transfusion. Occurrence of Intraoperative Transfusion. If such an episode occurs, then it will be defined as=1 'YES' If such an episode does not occur, then it will be defined as=0 'NO' [Time Frame: Intraoperative period]

Postoperative Complication. Occurrence of Postoperative Complication. If such an episode occurs, then it will be defined as=1 'YES' If such an episode does not occur, then it will be defined as=0 'NO'. [Time Frame: 1 month postoperatively]

Bowel Function Recovery. Postoperative time until the recovery of bowel function is achieved. Measurement unit: days. [Time Frame: 7 days postoperatively]

Length of Hospital Stay. Postoperative time that the patient can be safely discharged. Measurement unit: days. The patient will be discharged when it is ensured that is medically safe to be released. In particular, as the exit time of the patient, will be regarded the time that the patient will fulfil the Clinical Discharge Criteria. [Time Frame: Maximum time frame 39 days postoperatively]]

Negative Resection Margin. Occurrence of Negative Resection Margin. If such an episode occurs, then it will be defined as=1 'YES' If such an episode does not occur, then it will be defined as=0 'NO'. [Time Frame: 1 month postoperatively]

Local Recurrence Occurrence of Local Recurrence. If such an episode occurs, then it will be defined as=1 'YES' If such an episode does not occur, then it will be defined as=0 'NO'. [Time Frame: 5 years postoperatively]

Disease Free Survival. Occurrence of Disease Free Survival. If such an episode occurs, then it will be defined as=1 'YES' If such an episode does not occur, then it will be defined as=0 'NO'. [Time Frame: 5 years postoperatively]

Overall Survival. Occurrence of Overall Survival. If such an episode occurs, then it will be defined as=1 'YES' If such an episode does not occur, then it will be defined as=0 'NO'. [Time Frame: 5 years postoperatively]

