### *3.9 Calculation of the sample size*

Sample size calculation was based on the primary outcome. According to the literature [6] the percentage of mesocolic plane preservation in open and laparoscopic colectomy is 100% and 85.7%, respectively. Therefore, for  $\alpha=5\%$ , power=80%, 10% dropout rate, and 1:1 allocation ratio, the calculated sample in each group is 57 patients. Therefore, the total sample of the study is 114 patients.

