### *3.11 Blindness*

There will be no blindness at the level of the patient, the treating physicians (surgeon, anesthesiologist) and the researcher who will record the data.

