### *3.13 Monitoring*

Following hospital discharge, the patient will be called for reassessment one month after the operation to evaluate any postoperative complications. At the same time, the pathology report of the specimen and the adjuvant treatment will be recorded. In addition, at 5 years postoperatively, overall, disease-free survival and recurrence rates will be recorded.

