### *3.15 Study Group*

All participating members have years of experience in their field and have, therefore, completed the learning curve for the required techniques. Data collection and recording will be carried out by an independent, third party, researcher.

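### Five-year overall survival, disease-free survival and local recurrence are fixed as yes/no status with no dates called for, so a patient lost event-free before year 5 has no defined value

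*Protocol*

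**What the plan says.** Protocol section 3.8 lists three long-term outcomes, each scored 1 for yes and 0 for no with a time frame of five years: "Local Recurrence Occurrence of Local Recurrence", "Disease Free Survival. Occurrence of Disease Free Survival. If such an episode occurs, then it will be defined as=1 'YES" and "Overall Survival. Occurrence of Overall Survival". The same list defines bowel function recovery and hospital stay as durations in days, so a time scale is used there but not for the cancer outcomes.

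Section 3.13 gives the follow-up after discharge. First, "the patient will be called for reassessment one month after the operation to evaluate any postoperative complications". Then, "at 5 years postoperatively, overall, disease-free survival and recurrence rates will be recorded". No contact between these two points is specified, and no date of recurrence, death or last contact is requested.

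On who records the data, section 3.11 says "There will be no blindness at the level of the patient, the treating physicians (surgeon, anesthesiologist) and the researcher who will record the data", and section 3.15 says "Data collection and recording will be carried out by an independent, third party, researcher". Section 3.16 adds that data are held in patient charts and an electronic database. Section 2.1 names oncological results among the comparisons the trial is meant to make.

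**The concern.** A status at five years is known only for patients who had the event or were seen event-free at five years. Someone last known alive and disease-free at year 3 is neither a yes nor a no. The stated definition leaves two ways out: assign a code or drop the patient. A time-to-event definition would use the three years observed and then censor.

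This is more than an analysis detail awaiting a statistical analysis plan, because the protocol itself fixes the endpoint scale and the data to be captured. An analysis plan can add a rule for missing status, but it can censor only if the dates were collected, and nothing in 3.8 or 3.13 requires that.

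At stake are the five-year rates reported per arm, the use of any partial follow-up, and protection if loss differs between arms in amount or timing. Because the recorder is independent but not blinded, a code assigned without a rule would also be assigned with the arm known.

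**Working it through.** **Inputs.** From the protocol: 57 patients per group (3.9). A pooled normal-approximation calculation for 100% against 85.7%, two-sided 5% and 80% power, gives 50 per group; 50/0.9 = 55.6, so 56, close to the stated 57. Nothing below depends on that gap.

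Assumed, because the protocol gives neither figure: five-year survival S = 80% and loss L = 10% or 20%. The 10% borrows the dropout rate of 3.9 ("10% dropout rate, and 1:1 allocation ratio, the calculated sample in each group is 57 patients"), which was set for the one-month primary endpoint. Event times are exponential; loss is uniform over five years and independent of prognosis. The figures apply to OS and DFS, where yes means survival. No figure is offered for local recurrence.

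**Case A: events before loss are known, for example from charts.**

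λ = −ln(0.80)/5 = 0.0446 per year. The mean of exp(−λt) over 0 to 5 years is (1 − 0.80)/(5λ) = 0.8963.

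- Lost event-free = L × 0.8963
- Coded no: (1 − L) × S
- Coded yes: (1 − L) × S + lost
- Excluded: (1 − L) × S / (1 − lost)

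| Loss | Lost event-free | Excluded | Coded yes | Coded no |
|---|---|---|---|---|
| 10% | 0.0896 | 0.7200/0.9104 = 79.1% | 81.0% | 72.0% |
| 20% | 0.1793 | 0.6400/0.8207 = 78.0% | 81.9% | 64.0% |

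At 10% loss, 57 × 0.0896 = 5.1 patients per arm are affected. Their mean follow-up is 2.41 years, so about 12 person-years per arm go unused.

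**Difference between arms, in percentage points.**

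| Scenario | True | Excluded | Coded yes | Coded no |
|---|---|---|---|---|
| 85% vs 75%, 10% loss in both | 10.0 | 10.4 | 9.5 | 9.0 |
| 80% vs 80%, loss 5% vs 15% | 0 | +1.0 | −1.0 | +8.0 |
| 80% vs 80%, 10% loss in both, years 0–2.5 vs 2.5–5 | 0 | 0.9 | 1.0 | 0.0 |

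The 8.0 is 0.95 × 80 − 0.85 × 80 = 76.0 − 68.0. For scale, the standard error of the 85% vs 75% difference at 57 per arm is √[(0.85 × 0.15 + 0.75 × 0.25)/57] = 7.4 points. In simulations of 2,000,000 patients, Kaplan-Meier returned 79.96% to 80.02% in each of the 80% loss patterns of the last two rows, so its apparent difference is about 0.

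**Precision per arm.** The Kaplan-Meier standard error uses the Greenwood integral, S × √[(1/57) ∫ λ / (exp(−λt)(1 − Lt/5)) dt] over 0 to 5 years. Exclusion uses the binomial formula with p the excluded rate and 57 × (1 − lost) patients. At 10% loss the results are 5.4 and 5.6 points; at 20% loss, 5.6 and 6.1.

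**Case B: nothing is known before year 5 for lost patients.** At 10% loss, exclusion gives 0.72/0.90 = 80.0%, which is unbiased. Coding yes gives 0.72 + 0.10 = 82.0% and coding no gives 72.0%. No observed follow-up is wasted here.

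**The case against.** The strongest reply has four parts.

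- **Read literally, 3.13 describes case B.** If nothing is captured between month 1 and year 5, excluding lost patients is unbiased under independent loss and no follow-up is wasted. If the charts do hold dated contacts, an analysis plan can censor at them. This is partly right: information is not necessarily lost. But recovery then depends on dates that the protocol never requires.
- **Handling of missing data belongs to the analysis plan.** That is fair for the choice of test, estimator or imputation rule, and their absence is not the complaint. The endpoint scale and the data captured are fixed in the protocol, and those limit what an analysis plan can do.
- **The effect is small.** With equal loss the arm difference shifts by at most 1 point against a standard error of 7.4. The large figures need lost patients to be counted as failures, a rule the protocol does not state. This stands. So does the point that every survival and loss figure is assumed.
- **Dates would not blind the recorder.** True: the same person would record them. Dates remove the need to assign a code to an unknown status; they do not remove unblinded assessment of recurrence.

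It also stands that these are secondary endpoints on which the sample size was not based.

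**Conclusion.** The point holds as a weakness in how a stated objective is measured. The definitions in 3.8 give no value to a patient lost event-free before five years, and 3.13 does not secure the dates that would allow censoring.

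Under the stated assumptions, the rate reported per arm can vary by 9 points at 10% loss (72.0% to 81.0%) and by about 18 points at 20% loss (64.0% to 81.9%), depending on how such patients are coded. Most of that span comes from counting them as failures. The comparison between arms is little affected when loss is equal and independent of prognosis. It is materially biased, by 8 points in the example, only when loss is unequal and lost patients are coded as failures. The gain in precision from censoring is modest.

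With complete five-year follow-up the binary definitions suffice, but with no contact specified between month 1 and year 5 that cannot be assumed. The primary endpoint and the total of 114 patients are not touched. The change is worth making because it is cheap now and the dates may not be recoverable at year 5.

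**What to change.** In section 3.8, define OS as time from randomisation to death from any cause, and DFS as time from randomisation to recurrence or death, each censored at last contact. Report five-year Kaplan-Meier estimates with a log-rank or Cox comparison. Define local recurrence as time to local recurrence; cumulative incidence with death as a competing event is a reasonable option.

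In section 3.13, require three dates, taken from routine records: recurrence, death and last known status. State that the Kaplan-Meier estimates assume loss independent of prognosis.

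The cost is three database fields, revised wording in two sections, and some chart abstraction or telephone contact for patients followed elsewhere. The primary endpoint and the sample size stay as they are.

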### *3.9 Calculation of the sample size*

Sample size calculation was based on the primary outcome. According to the literature [6] the percentage of mesocolic plane preservation in open and laparoscopic colectomy is 100% and 85.7%, respectively. Therefore, for  $\alpha=5\%$ , power=80%, 10% dropout rate, and 1:1 allocation ratio, the calculated sample in each group is 57 patients. Therefore, the total sample of the study is 114 patients.

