There are three resection planes: the mesocolic, intramesocolic and muscularis propria plane. The ideal resection plane is the mesocolic, in which the colon is removed, along with the entire mesocolon and all the venous and lymphatic tissue, without violating the visceral fascia [4]. Surgical specimens categorized into either of the other two resection planes are associated with reduced R0 resection rates [6] and with reduced overall survival. Characteristically, the muscularis propria resection plane has been associated with up to 15% reduced survival rate compared to the mesocolic plane [7, 8].

There are specific morphometric characteristics of surgical specimens that are used to assess their quality. These include tumor and proximal colon high vascular ligation distance, number of lymph nodes, length of resected small bowel and colon, and total area of the mesocolon [7, 8]. These characteristics are directly related to the number of harvested lymph nodes and, therefore, to overall survival [7, 8].

According to initial results, CME specimens were larger in size, contained a longer length of colon, a larger mesenteric surface and a greater number of lymph nodes compared to the standard colectomy specimens [3]. In addition, a greater distance of the tumor from the resection margins was highlighted [3]. Specifically for right colon cancers, recent publications [6–8, 11–14] have shown that CME can achieve better morphometric specimen characteristics and a greater number of lymph nodes. In a recent randomized study, Di Buono et al. [15] compared the completion of CME or not, during laparoscopic right colectomy. A significant difference was found in favor of CME, regarding the specimen length and the lymph node harvest.

Despite these, the literature evidence regarding the morphological and qualitative characteristics of laparoscopic and open CME specimens are still inconclusive. Specifically for right colectomies, in the comparative study by Gouvas et al. [6], it was observed that the percentage of the mesocolic resection level was 100% in open colectomy, in contrast to 85.7% in the laparoscopic approach. However, this difference was not statistically significant. In a retrospective study by Ali Koc et al. [17], no difference was found between open and laparoscopic CME in terms of specimen length, R0 resection rate and number of resected lymph nodes. A recent

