publication by Ali Zedan et al. [18], argued that open CME is associated with longer specimens, larger mesenteric area, and increased resection margins. Another interesting finding was that the number of lymph nodes and the distance of the ligation site were greater in the laparoscopic CME group. However, the meta-analysis by Anania et al. [19] failed to validate any difference between the two methods in the total number of lymph nodes. Finally, a comparative analysis of our own series of patients did not show superiority of one technique over the other in terms of resection level, specimen length and number of lymph nodes [20].

Additional qualitative characteristics of a colon cancer operation include operative time, intraoperative blood loss, time of bowel function recovery, length of postoperative hospital stay, postoperative complications, as well as overall survival and local recurrence rate [2, 6, 8–10]. In a recent meta-analysis by Anania et al. [16] applying the principles of CME to right colectomies did not affect the rates of postoperative leaks, bleeding, overall complications, and reoperations. However, CME right colectomy was associated with optimal results in terms of 3-year overall survival and 5-year disease-free survival [16].

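### Is a total of 114 too few because section 3.9 plans on an open mesocolic-plane rate of exactly 100%?

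*Protocol*

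**What the plan says.** Section 3.7 makes the primary endpoint a yes/no outcome: whether the specimen was removed in the mesocolic plane. Section 3.9 sizes the trial on it. It takes from one comparative study that "the percentage of mesocolic plane preservation in open and laparoscopic colectomy is 100% and 85.7%, respectively". With a 5% significance level it then states "power=80%, 10% dropout rate, and 1:1 allocation ratio, the calculated sample in each group is 57 patients", so that "the total sample of the study is 114 patients".

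Section 1.1 reports the same two percentages from the same study and adds: "However, this difference was not statistically significant". It says more generally that "the literature evidence regarding the morphological and qualitative characteristics of laparoscopic and open CME specimens are still inconclusive", and that the unit's own series "did not show superiority of one technique over the other in terms of resection level". Section 3.15 says the participating team has "completed the learning curve for the required techniques". Section 3.9 names no formula, test or sidedness, and gives no alternative rates.

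**The concern.** An observed 100% is a sample proportion, and the true rate behind it may be lower. As a planning value it sits at the limit of the scale: that arm contributes no binomial variance, and the difference from 85.7% is as large as it can be. With the laparoscopic rate fixed, any error in the 100% can only raise the number needed. The background section treats the difference as unestablished, while the sample size section uses it as given and does not argue that 14.3 points is the smallest difference worth detecting.

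If open surgery in this unit achieves 97-99%, the trial would have less than its nominal power on the primary endpoint. A null result would then be hard to tell apart from too small a sample. Experienced laparoscopic surgeons might also do better than 85.7%, which would narrow the difference further.

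**Working it through.** **Inputs.** From section 3.9: open rate p1 = 1.00, laparoscopic rate p2 = 0.857, alpha 5%, power 80%, dropout 10%, allocation 1:1. Assumed: a two-sided test, because it reproduces the stated figure. Also assumed, for sensitivity only: open rates of 99%, 98% and 97%, with the laparoscopic rate held at 85.7%.

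**Reproducing 57 per group.** Let d = p1 − p2, let pbar be the mean of the two rates, and let (1.960 + 0.842)² = 7.849. Then

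n = 2 × pbar × (1 − pbar) × 7.849 / d².

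With pbar = 0.9285 and d = 0.143: n = 0.13278 × 7.849 / 0.020449 = 50.96, rounded up to 51. Dividing by 0.9 gives 56.7, rounded up to 57 per group, or 114 in total. This matches exactly. A common alternative (pooled and unpooled variances, no continuity correction) gives 50, then 56, a total of 112. The arithmetic in section 3.9 is sound.

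**Lowering the open rate, same formula.**

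| Open rate | n evaluable per arm | n with dropout | Total |
|---|---|---|---|
| 100% | 50.96 → 51 | 57 | 114 |
| 99% | 62.69 → 63 | 70 | 140 |
| 98% | 77.67 → 78 | 87 | 174 |
| 97% | 97.14 → 98 | 109 | 218 |

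**Power with 114 enrolled.** Formula power is Φ(d × √(n / (2 × pbar × (1 − pbar))) − 1.96). Exact power sums the binomial probabilities of all tables with p ≤ 0.05. The range runs from Fisher's exact test to the uncorrected chi-square test. The two columns for each method are 51 evaluable per arm (full 10% dropout) and 57 (none).

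| Open rate | Formula, 51 | Formula, 57 | Exact, 51 | Exact, 57 |
|---|---|---|---|---|
| 100% | 80% | 84% | 76-95% | 84-97% |
| 99% | 72% | 76% | 61-79% | 69-84% |
| 98% | 62% | 67% | 48-66% | 56-72% |
| 97% | 53% | 57% | 37-55% | 44-61% |

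**Reading the tables.** At the stated inputs the claim of 80% holds by the formula. Exact power is on either side of 80% at 51 per arm, depending on the test, and above 80% at 57 for both tests. At 99% the answer depends on the test and the dropout: the uncorrected chi-square keeps 79-84%, while Fisher's test gives 61-69%. At 98% and 97% power is below 80% in every column.

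**What 114 can detect.** If the open rate is 98%, 51 per arm reaches 80% formula power only when the laparoscopic rate is about 81% or lower, a difference of about 17 points.

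**The case for a change.** The strongest case for a change is this. One non-significant comparison does not establish a true rate of 100%. The unit's own series showed no superiority in resection level, and losing one or two points in the open arm raises the total from 114 to 140 or 174, that is by 23% (26/114) or 53% (60/114). Section 3.9 fixes these inputs, so the matter cannot be left to an analysis plan. It could be met without extra patients by stating what 114 can detect.

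The fragility stands, and at 98% or below it does not depend on the choice of test. The rest carries less weight.

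- Sections 1.1 and 3.9 do not contradict each other. Both give 100% and 85.7%. A non-significant earlier difference and inconclusive evidence are ordinary reasons to run a trial, and planning on a published estimate is accepted practice.
- A series that showed no superiority does not show that the open rate is below 100%. The protocol gives no rate from that series, so it offers no better planning value.
- The statement about experience in section 3.15 carries no rate either, and the protocol does not say that the surgeons in the cited study were less experienced.
- The figures at 51 per arm assume the full dropout. The endpoint is a property of the resected specimen, and section 3.13 has the pathology report recorded at one month, so loss after surgery should seldom remove it. The columns for 57 are at least as relevant.

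**Conclusion.** No change to the plan is needed. Section 3.9 delivers the power it states at the inputs it states, and those inputs are sourced and consistent across the protocol. The optimism is real: with the laparoscopic rate at 85.7%, formula power at 51-57 evaluable per arm falls to 62-67% at an open rate of 98% (exact 48-72%) and to 53-57% at 97% (exact 37-61%). At 99% it is 72-76% by the formula and 61-84% exact, so a claim that 99% requires 140 patients holds only under some choices of test.

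These figures rest on open rates that the protocol does not contain and on a formula and sidedness inferred from the 57 per group. Raising the total to 140, 174 or 218 would commit a single-centre trial to 26, 60 or 104 more patients on an assumption no better supported than the present one. Adding a sensitivity range or a detectable difference to section 3.9 would be informative, but it would change neither the data collected nor any result. A reader of a null result can judge from the estimated difference and its confidence interval what the trial has ruled out. This is a debatable planning choice and a fair trade-off, not an error.

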### *3.10 Randomization*

The randomization of the patients will be performed using a dedicated software with a 1:1 allocation ratio. The allocation group will be concealed with opaque envelopes that will be opened upon entrance of the patient in the operation theatre.

